5.3 Questionnaires

5.3.1 Patient Reported Outcomes (PROs)

Work productivity and work limitations will be assessed by the following instruments at visit 1, visit 7, and visit 13. Subjects will self-administer these instruments on paper. Site study personnel will review for completeness and enter responses into the eCRF.

5.3.1.1 *Work Productivity and Activity Impairment Questionnaire Specific Health Problem v2.0 (WPAI:SHP)*

The WPAI:SHP questionnaire (Appendix 2-1) assesses both work productivity through absenteeism (i.e., work time missed), presenteeism (i.e., impairment at work or reduced on-the-job effectiveness), and work productivity loss, as well as daily activity impairment (e.g., work around the house, shopping, exercising, childcare, studying) attributable to excess weight. WPAI:SHP outcomes are expressed as impairment percentages, with higher scores indicating greater impairment and less productivity, i.e., worse outcomes.

5.3.1.2 *Work Limitations Questionnaire 8-Item (WLQ-8) Self-administered Short Form*

The WLQ-8 questionnaire (Appendix 2-2) assesses the degree to which subjects have difficulty related to time management, physical tasks, mental/interpersonal tasks, and output tasks due to their physical and/or emotional health. The WLQ-8 produces subscale scores as well as an index of overall at-work productivity loss. WLQ-8 outcomes are expressed as proportion time with difficulty, with higher scores indicating greater limitations, i.e., worse outcomes.

5.4 Study Period

Subjects will be followed from baseline (month 0) to EOS at month 12 (visit 13), during which study clinicians or trained site personnel will collect study data and record them in the eCRF during monthly SMA study visits, including: weight as measured on a designated calibrated scale, pregnancy and serious adverse events (SAEs) (section 7), attendance at SMAs, and use of disallowed medications (section 5.2.2.3). PRO questionnaires will be completed as described in section 5.3. (Appendix 1-1)

Other than withdrawal of consent, subjects will remain in the study, and effort will be made to obtain a month 12 (visit 13) weight measurement from all randomized subjects regardless of SMA attendance or obesity treatment discontinuation during the study period. If a subject stops attending SMAs prior to EOS, he/she will be encouraged to attend visit 13 for a weight measurement within the visit window. Subjects who come back for a visit 13 weight measurement will also be asked to complete the PRO questionnaires during the visit and to report SAEs or disallowed medication use.

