6 STATISTICAL METHODS

6.1 Analysis Overview

Subjects will be randomized 1:1 to WMP + Rx or WMP alone. The data analyses for this study will be outlined in further detail in a Statistical Analysis Plan (SAP).

The significance level used in all statistical analyses will be 5% (two-sided).

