6.3 Sample Size Determination

6.3.1 Power and Sample Size for Primary Objective

Assumptions for sample size calculations included:

- Two sample two sided t-test with equal variances
- 5% significance level, but superiority is only claimed if estimated difference in mean weight loss favors WMP + Rx (this corresponds to a one-sided test on a 2.5% significance level).
- 1:1 randomization
- 50% of subjects in both arms are expected to drop out (based on input from the Cleveland Clinic)
 - Among subjects who drop out, 50% are expected to return for a month 12 (visit 13) assessment (retrieved drop outs).
 - Retrieved and non-retrieved drop outs in the WMP arm are assumed to have the same effect as subjects who complete the WMP arm.
 - Non-retrieved drop outs in the WMP + Rx arm are assumed to have an effect corresponding to subjects in the WMP arm.
 - Retrieved drop outs in the WMP + Rx arm are assumed to have an effect corresponding to half the weight loss difference (compared to WMP) of subjects who complete the study in the WMP + Rx arm.
- The following expected distribution of prescriptions in the WMP + Rx arm (based on input from the Cleveland Clinic):
 - 0% Orlistat (Xenical®)
 - 10% Lorcaserin/Lorcaserin extended-release (Belviq®/BelviqXR)
 - 30% Phentermine/Topiramate extended-release (Qsymia®)
 - 30% Naltrexone/Bupropion extended-release (Contrave®)
 - 30% Liraglutide 3.0 mg (Saxenda®)

Table 6-1 presents several sample size scenarios and power calculations based on the above assumptions, varying expected mean differences in weight loss between treatment arms (treatment effect) over 1 year and standard deviations (SD) as the variation of weight loss between subjects within the same treatment arm. Treatment effect scenarios of 3, 3.5, 4, and 5% were chosen based on product labels. SD of 8, 9, 10, and 11 % were chosen based on the NN8022 (SCALE) program [18] [19] [20] and the TRAMOMTANA [21] study.

Table 6-1. Power calculations for selected total N, treatment effects, and standard deviations

	Treatment effect (%)															
	3				3.5				4				5			
	SD (%)				SD (%)				SD (%)				SD (%)			
Total N	8	9	10	11	8	9	10	11	8	9	10	11	8	9	10	11
160	0.65	0.55	0.47	0.40	0.79	0.69	0.59	0.52	0.88	0.80	0.71	0.63	0.98	0.94	0.88	0.82
180	0.71	0.60	0.52	0.44	0.83	0.74	0.65	0.56	0.92	0.84	0.76	0.68	0.99	0.96	0.92	0.86
200	0.75	0.65	0.56	0.48	0.87	0.78	0.69	0.61	0.94	0.88	0.80	0.73	0.99	0.97	0.94	0.89

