240	0.82	0.73	0.64	0.56	0.92	0.85	0.77	0.69	0.97	0.93	0.87	0.80	1.00	0.99	0.97	0.94
300	0.90	0.82	0.74	0.65	0.97	0.92	0.86	0.78	0.99	0.97	0.93	0.88	1.00	1.00	0.99	0.98

Total N = sum of subjects in both treatment arms; treatment effect = difference in one-year weight loss of WMP + Rx compared to WMP alone; standard deviation (SD) = variation in weight loss between subjects within the same treatment arm.

Based on the above mentioned assumptions and results from the referenced studies, a 4% treatment effect and 10% SD is a conservative, yet realistic scenario. Therefore, a total sample size of 200 subjects (100 subjects per treatment arm) with 80% power for the confirmatory hypothesis assuming a 25% attrition rate over 12 months was chosen.

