8.2 Electronic Case Report Forms (eCRFs)

Study data prospectively collected at the study site will be entered into eCRF by trained site study personnel through a fully validated, 21 CFR 11 and HIPAA compliant EDC system. Subjects will complete PRO questionnaires on paper and the site study personnel will enter the completed forms into the EDC system. Site users will be provided eCRF Completion Guidelines (eCCGs) to assist with study data collection and entry. Study personnel will access the EDC system through a secure study website.

The study clinician has the ultimate responsibility for the collection and reporting of all study data through the eCRFs, as well as ensuring that they are accurate and complete to the extent possible.

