By regular activities, we mean the usual activities you do, such as work around the house, shopping, childcare, exercising, studying, etc. Think about times you were limited in the amount or kind of activities you could do and times you accomplished less than you would like. If PROBLEM affected your activities only a little, choose a low number. Choose a high number if PROBLEM affected your activities a great deal.

Consider only how much PROBLEM affected your ability to do your regular daily activities, other than work at a job.

PROBLEM had no effect on my daily activities	<hr style="display: inline-block; width: 300px; vertical-align: middle;"/>	PROBLEM completely prevented me from doing my daily activities
	0 1 2 3 4 5 6 7 8 9 10	

CIRCLE A NUMBER

Appendix 2-2: PRO Instruments – Work Limitations Questionnaire 8-Item Self-administered Short Form (WLQ-8)

CONFIDENTIAL

Work Limitations Questionnaire[©]

Self-Administered Online Short-Form

Work Limitations Questionnaire, © 1998, The Health Institute, Tufts Medical Center f/k/a New England Medical Center Hospitals, Inc.; [name].; Benjamin [name].; and GlaxoWellcome, Inc. All Rights Reserved.

Instructions

Health problems can make it difficult for working people to perform certain parts of their jobs. We are interested in learning about how your health may have affected you at work during the past 2 weeks.

- (1) The questions will ask you to think about your physical health or emotional problems. These refer to any ongoing or permanent medical conditions you may have and the effects of any treatments you are taking for these. Emotional problems may include feeling depressed or anxious.
- (2) The questions are multiple choice. They ask you to answer by placing a mark in a box.

For example:

- a. How satisfied are you with your local schools?

(Mark one box.)

Not At All Satisfied	
Moderately Satisfied	
Very Satisfied	

- b. How satisfied are you with your local police department?

(Mark one box.)

Not At All Satisfied	
Moderately Satisfied	
Very Satisfied	

These marks tell us you are very satisfied with your local schools and moderately satisfied with your local police department.

v05_20_2010

OPTIONAL PAGE

(3) Before you begin answering any questions, we would like you to write some information on the calendar.

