5.6.3 Supplementary Analyses

The analysis of % weight change will be complemented with the following supplementary analyses. Analyses #3 and #4 will assess the potential impact of altering the mode of administering the SMAs, from on-site to virtual, during the trial in response to the COVID-19 outbreak.

Supplementary Analysis #1 (Completer analysis)

In the context of this first supplementary analysis, the analysis population will be defined as subjects in the FAS with month 12 (visit 13) body weight data who adhered to randomized treatment up to and including visit 13. Adherence is defined as for the secondary estimand for the primary endpoint in Section 5.6.2, i.e., subjects in the WMP arm will be considered non-adherent if/when criterion 1 above is met and subjects in the WMP + Rx arm will be considered non-adherent if/when either criterion 1 or 2 above is met. As an example, a subject in the WMP + Rx arm that misses visit 10, 11, and 12, but attends all other visits and is covered by prescription claims for at least 80% of the planned study duration, is considered a completer in this context if month 12 (visit 13) weight data are available. This analysis will use the same ANCOVA model described for the primary estimand analysis of the primary endpoint (Section 5.6.1).

Supplementary Analysis #2

For the second supplementary analysis, the analysis population will be defined as subjects in the FAS who remain in the CC EHP for the entirety of their study participation. Subjects who leave the Cleveland Clinic Employee Health Plan (CC EHP) and end study participation or leave the CC EHP but continue to attend SMAs and take study medication if in the WMP + Rx arm will be excluded from the analysis. Analysis of this subset of subjects will include missing body weight data imputation as described in the Section 5.5.1. Change in percent body weight will be analyzed and presented as described for the primary estimand analysis of the primary endpoint (Section 5.6.1).

Supplementary Analysis #3

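### Weight has a retrieval route when visit 13 is missed, but PROs have no stated off-site route, and missing month 12 PROs are imputed from the WMP arm

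*Protocol*

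**What the plan says.** **Collection.** Protocol 5.3.1 schedules the WPAI:SHP and WLQ-8 at visits 1, 7 and 13: "Subjects will self-administer these instruments on paper". Protocol 8.2 agrees: "Subjects will complete PRO questionnaires on paper and the site study personnel will enter the completed forms into the EDC system". SAP 4.8.6 repeats paper at the same three visits. The WLQ-8 reproduced in Protocol Appendix 2-2 carries the title "Self-Administered Online Short-Form".

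**Missed visit 13.** Protocol 5.5 and footnote c of Appendix 1-1 give three steps for weight: call the subject in, take a recent value from the medical record, or accept a recent self-report. Neither place has a step for PROs. Protocol 4.1 encourages subjects who stopped SMAs to attend visit 13 for weight and questionnaires. Protocol 5.4 adds: "Subjects who come back for a visit 13 weight measurement will also be asked to complete the PRO questionnaires during the visit".

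**Virtual visits.** SAP 5.6.3 says that SMAs changed "from on-site to virtual, during the trial in response to the COVID-19 outbreak", and its third supplementary analysis treats the month 12 SMA as either on-site or virtual. SAP 7.0 limits the resulting changes to the primary endpoint. SAP 1.0 still rests on protocol version 1.0, which describes no virtual visits.

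**Missing PROs.** SAP 5.5.2 imputes each of the nine month 12 summary scores (five WLQ-8, four WPAI:SHP) in the way set out for weight in 5.5.1, where a model fitted to WMP-arm subjects fills gaps in both arms. SAP 5.7.1 plans no sensitivity analysis for secondary endpoints. SAP 5.8 reports PRO completion percentages but does not mention visit mode.

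**The concern.** The plan works to recover a month 12 weight from everyone, yet a subject whose weight comes from the medical record or a self-report can yield a weight and no PRO. That loss is avoidable. The questionnaires need no scale and no site procedure, and a subject who reports a weight is already in contact with the site.

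The imputation gives the loss a direction. SAP 5.5.1 justifies jump-to-reference imputation by assuming that the drug's added effect ends at discontinuation. That does not describe a WMP + Rx subject who attends by video and still takes the medication. If no form is obtained, that subject is scored as if the medication added nothing. Comparing the arms on PROs is a stated secondary objective (Protocol 2.2), and no planned PRO analysis looks at the move to virtual SMAs.

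**Working it through.** **1. The plan's own figure.** The only power statement is for weight. Protocol 6.3.1 says that "a 4% treatment effect and 10% SD is a conservative, yet realistic scenario", with 100 per arm and two-sided 5%, and gives 0.80. Recomputed power is 0.804 (noncentral t) or 0.807 (normal approximation), and all 80 cells of Table 6-1 reproduce within 0.005. No effect, SD or power is given for any PRO, so this figure does not bear on the gap.

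**2. Routes set side by side.**

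| Subject at month 12 | Weight | PROs |
|---|---|---|
| Attends on site | measured | paper form |
| Stopped SMAs, comes back | measured | asked at that visit |
| Weight from medical record or self-report | retrieved | no step stated |
| Virtual SMA | fallback in Protocol 5.5 if visit 13 counts as not attended | no route stated |

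**3. Inputs for the dilution.** From Protocol 6.3.1, stated for weight: 50% drop out; half of these return (25% retrieved, 25% not); non-retrieved WMP + Rx subjects have the WMP result; retrieved ones keep half the added effect. Carrying this pattern to PROs is an assumption. Let D be the added effect in WMP + Rx subjects who complete.

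**4. No loss from virtual visits.** The treatment-policy effect is 0.50 × D + 0.25 × 0.5D + 0.25 × 0 = 0.625D. The 75% with data average 0.625D / 0.75 = 0.833D. Imputing the other 25% at zero added effect gives 0.75 × 0.833D = 0.625D. On the plan's own assumptions nothing is lost at this stage.

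**5. Avoidable loss.** Suppose a share v of the assessable 75% in the WMP + Rx arm has no form, at random. The estimate becomes 0.75 × (1 − v) × 0.833D = 0.625D × (1 − v), so the retained share is 1 − v.

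| v (assumed) | Retained share |
|---|---|
| 20% | 80% |
| 30% | 70% |
| 50% | 50% |

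**6. Simulation of the mechanism.** Settings: 100 per arm, ANCOVA, regression imputation from the WMP arm on one baseline covariate, Rubin pooling, 30 imputations, 600 runs. Assumptions: standardised effect 0.40 (borrowed from weight, 4/10), equal random missingness in both arms, and missing subjects keep the effect.

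| Missing | Effect retained | Power | Power, observed cases only |
|---|---|---|---|
| about 0% | 1.01 | 0.81 | 0.81 |
| 25% | 0.76 | 0.47 | 0.72 |
| 40% | 0.60 | 0.20 | 0.55 |
| 50% | 0.51 | 0.09 | 0.52 |

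The retained share follows one minus the missing share in the WMP + Rx arm. With 50% missing in the WMP arm only, the ratio is 0.99, so there is no dilution. The power columns illustrate the mechanism and are not forecasts for this trial, because the PRO effect is assumed.

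**7. Scope.** SAP 5.5.2 specifies imputation at month 12 only. The secondary-estimand MMRM (SAP 5.7.2.2) uses observed assessments while adherent and does not borrow from the WMP arm. There, missing forms cost precision and may bias.

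**The case against.** The strongest reply is that the documents fix the medium and not the place. A paper form posted to the subject would comply with Protocol 5.3.1 and 8.2. The sentence on completing forms at the visit concerns only subjects who stopped SMAs and return. The first step in Protocol 5.5 calls the subject into the office, and Protocol 5.4 then asks for the questionnaires. SAP 5.6.3 says that SMAs went virtual; it does not say that on-site weighing or form completion ended. All of this stands. A reader might infer that PROs could be given only on site, or that virtual attendees could not give them. The text supports only that no route is stated.

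A reader might also count the planned 25% attrition as damage and conclude that 60%, 52.5% or 37.5% of the effect survives at v = 20%, 30% or 50% (from 1 − (0.25 + 0.75v)). That treats non-retrieved drop-outs as keeping the full drug effect, whereas the plan's sizing assumes for weight that they keep none of it. Step 4 shows that no loss arises there on that assumption.

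The WLQ-8 title belongs to the instrument and does not show that this trial had an online route. Nor can protocol version 1.0 be faulted for not foreseeing virtual visits; that part of the gap lies in the SAP, which was revised after the change.

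The reply does not remove two facts. Weight has off-site fallback steps and PROs have none. And the SAP kept both paper collection and WMP-based imputation when it added the virtual-SMA analyses for weight.

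**Conclusion.** The point holds as a cheap improvement. Followed as written, the plan can recover a weight from the medical record or self-report and leave the PRO missing. It states no PRO route for virtual attendees at visits 7 or 13. Each avoidable missing month 12 form from a WMP + Rx subject still on treatment moves the primary-estimand comparison towards no difference.

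The retained share is about 1 − v. This rests on forms being lost at random among otherwise assessable WMP + Rx subjects and on the weight drop-out pattern holding for PROs. The documents do not give v, so the actual size cannot be computed.

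It would go too far to say that every PRO analysis is diluted. The effect is confined to the month 12 primary-estimand analyses, and it needs both a real PRO effect and missing forms in the WMP + Rx arm. SAP 3.2 makes all secondary endpoints supportive, so the confirmatory test on weight is untouched.

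**What to change.** **Collection (Protocol 5.3.1, 5.4, 5.5 and 8.2).** Within the visit 7 and visit 13 windows, send both questionnaires by mail or secure electronic form to every subject who has not withdrawn consent and is not seen on site. Include those whose weight comes from the medical record or self-report. Record the mode of completion. Reconcile the paper wording with the online title of the appended WLQ-8.

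**Reporting (SAP 5.8).** Report PRO completion by arm and by visit mode, and state how forms were obtained at visits held virtually.

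**Analysis (SAP 5.7.1), for visits already held.** Add a PRO sensitivity analysis that imputes on-treatment subjects with missing forms from their own arm under missing at random. The adherence criteria in SAP 5.6.2 could define on-treatment. Keep the planned analysis as it is for subjects who stopped treatment.

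**Cost.** Protocol wording, a mailed or electronic form, and a little more analysis. The downside is a possible mode-of-completion difference. It may not be equal between arms, because the arms attend separate SMA groups (Protocol 5.2.2.1); that is a reason to record the mode. New collection cannot recover forms from visits already past, which is why the sensitivity analysis is also needed.

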4 STUDY DESIGN

4.1 Overview

This is a one-year, single-center, randomized, open-label, parallel-group PCT comparing Cleveland Clinic's existing Integrated Medical WMP combined with medication for chronic weight management versus Cleveland Clinic's existing Integrated Medical WMP with no medication for weight management in subjects with obesity. Subjects will be randomized 1:1 to receive either Cleveland Clinic's Integrated Medical WMP with medication for chronic weight management ("WMP + Rx") or Cleveland Clinic's Integrated Medical WMP alone ("WMP").

To ensure that the study setting is as close to real-world as possible, the weight management program provided to all study subjects will be similar to the Integrated Medical WMP that is currently offered by the Cleveland Clinic. In this program, SMAs are covered by the Cleveland Clinic Employee Health Plan and employees are responsible for a co-payment.

In the WMP + Rx arm, obesity medications approved by the FDA for chronic weight management listed in Table 5-1 are allowed. Selection of specific medication is at the discretion of the study clinician. Subjects randomized to the WMP + Rx arm will pay a fee for the medication, simulating the co-payment that would be applied if the Health Plan covered treatment with medications for chronic weight management.

Total study duration for the individual subjects will be approximately one year. Subjects will be followed and data collection will continue for the full duration of the study, unless the subject withdraws informed consent. The full duration of the study is defined as up to and including visit 13.

Study visits include an individual screening and randomization visit (visit 1; informed consent must be obtained at visit 1 before screening), followed by twelve once-monthly visits set up in the context of SMAs (visit 2 to visit 13; further described in Section 5.2.2.1). All subjects will be referred to a nutritionist appointment between visit 1 and visit 2. End of Study (EOS) is visit 13 (month 12 (-14 days, +28 days)) (section 5.5). Effort will be made to obtain a month 12 (visit 13) weight measurement from all randomized subjects. Subjects who potentially have stopped attending the SMAs prior to EOS will be encouraged to attend visit 13 for a weight measurement

and completion of questionnaires within the visit window, unless they have withdrawn consent. There will not be a follow-up period.

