5.2.2.3 Concomitant medications

Concomitant medications for medical conditions other than obesity are allowed in both treatment arms at the discretion of the study clinician, except for the use of glucagon-like peptide-1 receptor agonists (GLP-1 RAs) and sodium-glucose co-transporter 2 (SGLT-2) inhibitors for diabetes diagnosed during the study. Other than the medication prescribed by the study clinician for chronic weight management in the WMP + Rx arm (section 5.2.2.2), use of any medication, on- or off-label, for weight loss purposes is not allowed in either arm during the study. Through routine medication review during SMA study visits, use of medications that are not allowed per protocol (i.e., “disallowed”) will be identified and will be indicated in the eCRF. The subject will remain in the study.

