5.5 End of Study (EOS)

EOS is defined as 12 months (-14 days, +28 days) after baseline.

If a subject does not attend visit 13, a stepwise approach to obtaining weight will be implemented according to the following hierarchy:

1. Subject called into office for month 12 weight measurement (-14 days, +28 days from scheduled month 12/visit 13).
2. Recent (-14 days, +28 days from scheduled month 12/visit 13) weight extracted from the electronic medical record (EMR).

3. Recent (-14 days, +28 days from scheduled month 12/visit 13) subject-reported weight used.

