7.2.1 Reporting Period of Serious Adverse Events (SAEs)

SAEs will be reported from randomization until EOS at month 12, or until the subject withdraws from the study. Study clinicians will follow SAEs that occur in any subject during this study in a manner consistent with routine clinical practice.

The study clinician is responsible for alerting Novo Nordisk or its designee to any SAE within 24 hours of becoming aware of it via electronic data capture (EDC) entry. The subject should be followed until the outcome of the event is closed out. Follow-up information should be reported within 24 hours of it becoming available. Requests for follow-up information should be resolved within 14 calendar days.

The study clinician is responsible for assessment of causality and outcome of SAEs, as defined in Appendix 3. Causality and outcome should be provided at the time of reporting an SAE.

If an investigator becomes aware of SAEs after EOS at end of month 12, that are possibly related to the study product, these should be reported as spontaneous events.

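### After the last attended visit, nothing requires SAE, pregnancy or disallowed-medication status to be sought in subjects whose month 12 weight comes from the EMR or self-report, or is not obtained

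*Protocol*

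**What the plan says.** **Where the items are collected.** Under Protocol 5.4, site staff "collect study data and record them in the eCRF during monthly SMA study visits"; the list covers weight, pregnancy, SAEs, attendance and disallowed medication. The Time and Events Schedule (Appendix 1-1) places adverse events and disallowed medication at the same visits. Protocol 5.2.2.3 finds disallowed drugs the same way: "Through routine medication review during SMA study visits, use of medications that are not allowed per protocol" is to be identified and entered in the eCRF.

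**Catch-up for subjects who stop attending.** Protocol 5.4 covers those who return for a visit 13 weight. They "will also be asked to complete the PRO questionnaires during the visit and to report SAEs or disallowed medication use".

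**Other routes to the month 12 weight.** Protocol 5.5 states: "If a subject does not attend visit 13, a stepwise approach to obtaining weight will be implemented according to the following hierarchy". Step 1 calls the subject into the office, step 2 takes a weight from the EMR and step 3 uses a weight the subject reports. Appendix 1-1 footnote c repeats the three steps. Neither place mentions SAEs, pregnancy or medication.

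**How long reporting runs.** Protocol 7.2.1 states: "SAEs will be reported from randomization until EOS at month 12, or until the subject withdraws from the study". Protocol 7.3.1 sets the same period for pregnancies. Under 5.7.2 only withdrawal of consent ends participation, and 4.1 says "data collection will continue for the full duration of the study" unless consent is withdrawn. Section 7.2.1 also requires an SAE to be reported within 24 hours of the clinician learning of it.

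**How the data are used.** SAP 6.5 summarizes SAEs descriptively by SOC and PT, with no formal safety analysis. SAP 5.9 tabulates disallowed medication.

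**The concern.** The reporting period covers every subject who has not withdrawn consent, but the scheduled questions cover only those who attend. The authors saw the need for a catch-up question and wrote one for subjects who return in person. They wrote none for steps 2 and 3, although the site is then already in the record or obtaining information from the subject.

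SAEs are the only adverse events that must be collected (Protocol 7.1, SAP 6.1), so this is nearly all of the trial's safety data. An event nobody asked about leaves no entry in a table by SOC and PT and reads as no event. A subject who stopped attending because of a serious event could be among those missed. In WMP + Rx, attendance and prescription coverage are separate adherence criteria (SAP 5.6.2), so a subject can leave the SMAs and still fill prescriptions. In an open-label trial the reasons for leaving may also differ by arm.

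**Working it through.** **Which routes carry a question**

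| Month 12 situation | SAE and medication question required? |
|---|---|
| Attends visit 13, including a virtual SMA | Yes, as at any visit (5.4, Appendix 1-1) |
| Step 1: called in for a weight | Yes, the 5.4 catch-up applies |
| Step 2: weight from the EMR | None stated |
| Step 3: weight reported by the subject | None stated |
| No weight found, consent not withdrawn | None stated |
| Consent withdrawn | Not applicable; collection ends (5.7.2) |

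**How many subjects**

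Inputs:
- 200 randomized and 150 expected to have an on-site final weight (Protocol 4.2.5).
- "50% of subjects in both arms are expected to drop out" (Protocol 6.3.1), half of whom are expected to return for month 12 (same section).

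The plan's figures agree with each other: 200 × 0.50 × 0.50 = 50 not retrieved, and 200 − 50 = 150. Also 50/200 = 25%, the attrition rate given in 6.3.1. Fifty is an upper bound for the last two rows marked none stated together with step 2. It includes consent withdrawals, and the plan does not split the rest into EMR weight, self-reported weight and no weight.

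**How much person-time**

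The documents give no timing of drop-out, so let *k* be the month of the last attended visit (assumed).

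Share with no scheduled question = 50 × (12 − *k*) / (200 × 12)

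| *k* | Person-months of 2400 | Share |
|---|---|---|
| 11 | 50 × 1 = 50 | 2.1% |
| 9 | 50 × 3 = 150 | 6.3% |
| 6 | 50 × 6 = 300 | 12.5% |
| 3 | 50 × 9 = 450 | 18.8% |
| 0 | 50 × 12 = 600 | 25% (ceiling) |

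**What that could mean in events**

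The plan gives no SAE rate, so assume a constant one. At 5% per year, 200 × 0.05 = 10 SAEs are expected. The number in unqueried time runs from 10 × 0.021 = 0.2 (*k* = 11) to 10 × 0.25 = 2.5 (*k* = 0). At 2% it is 0.1 to 1.0 of 4, and at 10% it is 0.4 to 5.0 of 20. These are the misses if nothing is learned by other routes; if everything is, the miss is zero.

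**Illustration of an imbalance between arms**

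The plan assumes equal drop-out. Suppose instead that non-retrieval is 15% in one arm and 35% in the other, with *k* = 3, 5 true SAEs per arm and no other capture. The expected counts are 5 × (1 − 0.15 × 0.75) = 4.44 and 5 × (1 − 0.35 × 0.75) = 3.69. Equal true rates would then show a count ratio of 4.44/3.69 = 1.20, or 0.83 with the arms exchanged.

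**The case against.** - **Questions before drop-out.** A reader might infer that these subjects are never asked about SAEs. They are asked at every SMA they attend; the gap runs only from the last attended visit to month 12.
- **Capture outside visits.** The 24-hour rule in 7.2.1 is not tied to a visit, and WMP + Rx subjects who suspend or stop medication are asked to tell the study clinician (5.2.2.2). Some events will surface this way. This stands, but it depends on the clinician happening to learn of the event. Section 5 allows extraction from medical records, but words it as at each study visit.
- **Silence is not a prohibition.** Section 5.5 describes how to obtain a weight. It does not stop the site recording an SAE seen or mentioned on the way, and 7.2.1 would then require it. This stands too: the procedure is unspecified, and it would go too far to say that 5.5 contradicts 7.2.1 or 4.1.
- **Virtual visits.** SAP 5.6.3 foresees virtual month 12 SMAs. A subject at one is at a study visit, so a self-reported weight need not mean that no question was asked. The documents do not say how weight was obtained at those visits.
- **Existing summaries.** Attendance by arm, disposition with reasons for not completing, and missing counts for visit data (SAP 5.7.1.2, 5.2, 4.1) let a reader gauge incomplete follow-up. They do not show whose SAE status was ascertained to month 12.
- **Bias.** A reader might infer that the SAE comparison is biased, or that rates rest on all randomized subjects. No formal comparison is planned, no SAE denominator is stated, and unequal non-retrieval is an assumption made here.

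**Conclusion.** The gap is real but limited. Scheduled questions stop with attendance, the catch-up reaches only those who return in person, and steps 2 and 3 of 5.5 seek weight alone. Under-counting of SAEs is a risk and has not been shown.

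It concerns at most about 50 of 200 subjects, fewer once consent withdrawals and virtual month 12 attendance are taken out. In person-time it is about 6%, 12.5% or 19% for an assumed last visit at month 9, 6 or 3, with a ceiling of 25%. These shares rest on the plan's drop-out figures and on assumed timing. The number of events lost, and any difference between arms, cannot be derived from the documents.

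The effect falls on the descriptive safety and disallowed-medication summaries. A reader might carry it over to the primary result, but the documents do not support that. SAEs do not enter the weight analysis, disallowed medication is not an adherence criterion (SAP 5.6.2), and the primary estimand applies regardless of adherence. This is a low-cost improvement worth making, and the trial's main conclusion does not depend on it.

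**What to change.** 1. **Protocol 5.5 and Appendix 1-1 footnote c.** State that at the step 3 contact the site also asks the SAE, pregnancy and disallowed-medication items. State that at step 2, and for any other subject who missed visit 13, has not withdrawn consent and has the EMR searched for a weight, the site reviews the same record for these items from the last attended visit to EOS.
2. **SAP 6.5.** Report by arm, next to the SAE counts, the number of subjects whose SAE status was ascertained through EOS. The SAP change log shows that the trial had already started by SAP version 2. This row is useful even if conduct can no longer be changed.

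**Cost.** One protocol sentence, one footnote and one table row, with extra record review or questions for up to about 50 subjects by existing site staff. Each SAE found also needs a causality and outcome assessment (7.2.1, Appendix 3), and the added review departs slightly from the aim of staying close to routine care. The EMR may miss care given elsewhere, so ascertainment would improve without becoming complete.
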